All EAs will be notified to the local EC by the study coordinator at each centre using their own form. EAs shall also be reported to the coordination of the proposing institution no later than 7 days after notification of the EA.

In the case of adverse events related to bcg vaccine (ulcer with diameter greater than 1 cm, cold subcutaneous abscess, hot subcutaneous abscess, granuloma, regional lymphadenopathy not suppurated greater than 3 cm, suppurated regional lymphadenopathy, cheloid scar or lupoid reaction), the coordination of the proposing institution should be notified to the National Immunization Program of the Ministry of Health.

Serious adverse events (EAG) should be reported immediately to the coordination of the Proposing Institution through telephone contact. From this notification, the EAG must be reported to ANVISA within a maximum of 24 hours by the coordinator of the proposing institution through the agency's electronic portal (Notification Form of Serious Adverse Events in Clinical Trials available on the Electronic Portal of Anvisa > Medicamentos > Clinical Research > Adverse Events > Form for Notification of Serious Adverse Events in Clinical Trials - Notification EC).

All serious adverse events suspected to have been caused by the proposed experimental treatment, including deaths will be reported to CONEP, through notification and within 24 hours.

There will be a review of The EA data every 2 weeks. If adverse events are unexpected or not previously described, case review will be requested through a meeting of the data monitoring and security committee, which should take place in real time by videoconference. Serious adverse events will be immediately flagged to the CMDS for extraordinary analysis also by real-time videoconferencing.

Criteria for discontinuation of the study for safety reasons:

No formal rule will be adopted to interrupt the study for safety reasons. The CMDS may recommend stopping the study, based on the review of interval safety results. The study can only be canceled or discontinued after analysis of the reasons for discontinuity by the institution's ZIP Code or CONEP.

Criteria for discontinuation of experimental treatment in the participants:

No formal rule will be adopted to discontinuation of experimental treatment in the study participants. The CMDS may recommend this study interruption, based on the review of interval results as described above. Nevertheless, this decision can only be effected after evaluation and approval by the institution's ZIP Code or CONEP.

QUALITY MANAGEMENT:

All studies will be conducted in accordance with the ICH-GCP Guidelines (ICH-GCP E6 R2), as far as possible in the research environment, as well as all national legal and regulatory requirements (as applicable).

BUDGET:

Cost	Value
Legal entity	R\$84,000.00
Bags	R\$160,800.00
Inputs	R\$297,188.57
Other	R\$43,571.43
Capital	R\$14.440,00
Total	R\$600,000.00

SCHEDULE:

The schedule presented below is a schedule, and the study should be started only after approval of the CEP.

Phase	Beginning	End
Submission of amendment to CEP/CONEP	01/08/2021	31/08/2021
Recruitment/Inclusion/Intervention	30/10/2020	31/12/2021
Follow-up of patients	30/10/2020	31/06/2022
Data analysis	31/06/2022	31/09/2022
Reporting/Results	31/09/2022	31/12/2022

REFERENCES:

- Brazil, Ministry of Health 2020. Available in: <https://coronavirus.saude.gov.br/definicao-de-caso-e-notificacao>. Access on 05 February 2021
- Brazil, Ministry of Health 2021. Technical Report - National Vaccination Campaign against Covid-19
- Butantan, 2021. BULLText SAYINGS - HEALTH PROFESSIONAL - Covid-19 adsorbed vaccine (inactivated)
- ANVISA, 2021. VACCINE COVID-19 (RECOMBINANT) INSTITUTE OF TECHNOLOGY IN IMMUNOBIOLOGICALBIO-MANGUINHOS / FIOCRUZ. Available in: https://www.gov.br/anvisa/pt-br/assuntos/noticias-anvisa/2021/bulas-saiba-mais-sobre-as-vacinas-autorizadas-para-uso-emergencial/bula-vacina-covid-19-recombinante_vps_001_21-01-2021.pdf. Access on 12 D February 2021
- Kritski, A; Alves D; G Werneck; Zimmermann, I; M Sanchez; Galliez R; Medronho R. Technical Note from researchers from the Federal University of Rio de Janeiro

(UFRJ), University of São Paulo (USP) and University of Brasília (UnB) March 25, 2020 PANORAMA OF COVID-19. Available in <https://ufrj.br/sites/default/files/img-noticia/2020/03otatecnica25032020.pdf> Last access on April 23, 2020

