This project presents an innovative proposal, addressing a BCG vaccine with known efficacy against severe TB in childhood and reliable for the use of adjuvant therapy in patients with malignant bladder neoplasia.

BCG is an easily accessible vaccine, widely used by SUS in newborn children, thus facilitating its incorporation into a new preventive proposal for COVID-19. In addition, the selection of health professionals will be based on diagnostic screening and confirmatory tests of COVID-19.

It is intended to analyze the role of BCG in the prevention of infection and also in the occurrence of severe forms of COVID-19 in addition to evaluating the immune response mediated by this vaccine in voluntary health professionals.

GOALS:

In the period of 6 months, to analyze the effect of BCG as a protective factor for COVID-19 in research volunteers, aiming at greater efficiency in the prevention of subjects at high risk of infection and evolution to severe forms of the disease, as well as to evaluate the specific and non-specific immune responses to SARS-CoV-2 in vaccinated and unvaccinated volunteers who evolved with COVID-19 or not.

Primary Objectives:

1. Assess the impact of BCG vaccine administration on the cumulative incidence of SARS-CoV-2 infection
2. Assess the impact of BCG vaccine administration on the cumulative incidence of severe forms of COVID-19
3. Evaluate the bcg vaccine-mediated immune response in volunteers

Secondary Objectives:

In groups receiving BCG or placebo, infected and not infected with SARS-CoV-2:

- Epidemiological:

1. Estimate whether BCG vaccination compared to placebo prolongs the time to the first respiratory disease proven by SARS-CoV-2;
2. Estimate whether BCG vaccination compared with placebo reduces the proportion of symptoms associated with COVID-19 (fever or at least one sign/symptom of respiratory disease);
3. Estimate whether BCG vaccination compared to placebo reduces absenteeism (missing days) in volunteers who are health professionals;
4. Analyze the safety of BCG vaccination in adult volunteers;

- Laboratories:

5. Describe the inflammatory profile by dosing neutrophils, platelets, cit-H3, alpha 1 antitrypsin (α 1AT), galectin-2, ferritin, transferrin-R, glycated hemoglobin (HbA1c),

C-reactive protein (CRP), D-dummer, LDH, albumin and hemosedimentation velocity (ESR);

6. Describe the profile of inflammatory cytokines identified in the BCG and placebo groups, comparing to the protective events to SARS-CoV-2;

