7. Describe the epigenetic alterations associated with monocytes and neutrophils related to the protection of COVID-19;
8. Characterize the cell population (T, B lymphocytes, neutrophils and monocytes) in peripheral blood of the study groups (BCG and placebo);
9. Relate the profile of immune response associated with mild and severe forms observed in the study groups (BCG and placebo);
10. Analyze the serum concentration of antibodies and relate it to the immune response;
11. Identify possible antibodies that may confer immunity to new COVID-19 infections;
12. Perform transcriptomic analysis of neutrophilic, lymphocytic and monocytic responses in the study groups (BCG and placebo) involved in the modulation of immune responses in the study groups;
13. Identify predictive biomarkers of infection and/or illness by SARS-CoV-2;
14. Develop a predictive model of infection and/or illness by SARS-CoV-2;
15. Identify socio-demographic factors, life habits, associated diseases and previous vaccinations associated with immune response and the risk of COVID-19 infection.

With a view to the approval of specific vaccines against COVID-19 for emergency use by ANVISA in January 2021 and incorporated by the National Immunization Program of the Brazilian Ministry of Health, the objectives for the subgroup of individuals who receive the intervention of this study with BCG or placebo and who are also immunized with specific vaccines against COVID-19 will be carried out in the part, taking into account in the future analysis, the time between the intervention of the study and vaccination against COVID-19, the vaccine used and the performance of the second dose of the vaccine used, aiming to identify a possible adjuvant effect of bcg vaccine as a stimulant

of cellular immunity, which also plays a role in immunopathogeny against SARS-CoV-2, including action prior to humoral response.

Furthermore, in cases of participants immunized with specific vaccines against SARS-CoV-2, the identification of asymptomatic infection by the virus, diagnosed through the conversion of serologies to COVID-19 in the moments M3 and M6 after the intervention, will not be evaluated, considering the bias caused by the use of vaccines against viral disease. In these cases, in order to characterize the diagnosis of COVID-19, there will be a need for a report (self-reported) of characteristic signs/symptoms associated with detection of SARS CoV-2 by RT-PCR.

METHODOLOGY:

Study Definitions:

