The definitions of the Brazilian Ministry of Health (Brazil, 2020) will be used:

Flu syndrome (GS): Individual with acute respiratory condition, characterized by at least two (2) of the following signs and symptoms: fever (even if reported), chills, sore throat, headache, cough, runny nose, olfactory disorders or taste disorders.

Severe Acute Respiratory Syndrome (SARS): Individual with **GS** sit : dyspnea/respiratory distress OR persistent pressure in the chest OR O2 saturation less than 95% in room air OR bluish coloration of the lips or face.

Confirmed cases of COVID-19:

- **By clinical criterion:** Case of GSs or SRAG with clinical confirmation associated with anosmia (olfactory dysfunction) OR ageusia (gustatory dysfunction) acute without other previous cause.
- **Por clinical - epidemiological criterion:** Case of GSs or SRAG with a history of close or household contact, in the 14 days prior to the appearance of signs and symptoms with case confirmed for COVID-19.
- **By clinical criterion - imaging:** Case of GSS or SRAG or death from Rags that could not be confirmed by laboratory criterion And that presents at least one (1) of the following tomographic changes:
 - Peripheral, bilateral , **horizontal matte glass opacity** , with or without consolidation or visible intralobular lines ("paving"), **OR**
 - **Multifocal frosted glass** opacity of rounded morphology with or without consolidation or visible intralobular lines ("paving"),**OR**
 - **Reverse halo sign** or other findings of organizing pneumonia (later observed in the disease).
- **By laboratory criterion:** Case of SG or SRAG with test of:
 - **Molecular biology:** detectable result for SARS-CoV-2 performed by the RT-PCR method in real time.

- **Immunological:** reactive result for IgM, IgA and/or IgG performed by the following methods: Enzyme-Linked Immunosorbent Assay (ELISA); Immunochromatography (rapid test) for antibody detection; Electrochemiluminescence Immunoassay (ECLIA);

- **Antigen Research:** reagent result for SARS-CoV-2 by immunochromatography method for antigen detection.

- **By laboratory criterion in asymptomatic individual:** Asymptomatic individual with test results:

- **Molecular Biology:** detectable result for SARS-CoV-2 performed by the RT-PCR method in real time;

- **Immunological:** reagent result for IgM and/or IgA performed by the following methods: ELISA or Immunochromatography (rapid test) for antibody detection.

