4. Have not received a specific vaccine against COVID-19 or, if vaccinated against SARS-CoV-2, have received the complete immunization schedule only with vaccines approved by ANVISA and implemented by the National Immunization Program, (including the second dose) within a minimum of 15 days prior to the date of inclusion in the study
5. If the participant have not received a specific vaccine against COVID-19 approved by ANVISA, be aware and agree to be able to receive them only 15 days after the intervention proposed in this study

Exclusion criteria:

1. Professionals with a history of sars-cov-2 confirmed infection through RT-PCR or who have already presented clinical and molecular diagnosis of COVID-19 prior to the study

2. Individuals who have not undergone confirmatory tests for COVID-19
3. Breastfeeding
4. Individuals who report having primary or acquired immunodeficiency
5. Individuals who report being affected by malignant neoplasms
6. Patients reporting treatment with high-dose corticosteroids (equivalent to the prednisone dose of 20 mg/day or more) for more than two weeks
7. Patients who report being on other immunosuppressive therapies (antineoplastic chemotherapy, radiotherapy, among others)
8. Individuals who report being diagnosed with autoimmune diseases
9. Dermatological conditions at the vaccine site or generalized
10. Individuals who report being treated for active tuberculosis
11. Individuals who report a history of previous treated tuberculosis
12. Individuals with febrile symptoms (body temperature $\geq 37.5^{\circ}\text{C}$ in the last 48h)
13. Participation in other clinical prevention trials for COVID-19 (vaccines already approved by ANVISA for use by the National Immunization Program are not included in this item)
14. Report of vaccination with live microorganism administered in the month prior to randomization
15. Require that, if another vaccination with live microorganism is required, it is administered in the month following randomisation (If the other live vaccine can be administered on the same day, this exclusion criterion does not apply)
16. Known anaphylactic reaction to any ingredient in bcg vaccine
17. Adverse reaction prior to BCG vaccine [significant local reaction (abscess) or suppurative lymphadenitis]
18. BCG vaccine administered in the last year

Intervention Plan:

Intervention:

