Randomly eligible participants who have provided informed written consent will be recruited. Participants will then be allocated to one of the study regimens in a ratio of 1:1.

1. **Intervention:** BCG vaccine, single dose
2. **Control regimen:** placebo, single dose.

In the BCG clinical trial, participation in the study will last 6 months: during the first 4 months, or for the duration of the recruitment period, participants will receive the randomly designated BCG regimen or only control group. After the recruitment period, all study participants should have received BCG or placebo, and both groups will be monitored through clinical and laboratory examination for 6 months of follow-up. Biosafety care to combat COVID-19 adopted in the participating Health Units will also be monitored during the study period.

Comparator:

The natural evolution of SARS-CoV-2 infection in health professionals will be used to evaluate the efficacy of bcg use as preventive therapy, considering the use of specific vaccines against COVID-19, the time of positivity of COVID-19 tests and the evolution to severe forms of COVID-19.

Specific vaccines against SARS-CoV-2:

- Coronavac® (Sinovac® / Butantan Institute):

The vaccine developed by the Sinovac laboratory® in partnership with the Butantan Institute is a vaccine containing the inactivated SARS-CoV-2 virus. Seroconversion studies of the Sinovac/Butantan vaccine showed results of >92% in participants who took both doses of the vaccine within 14 days and > 97% in participants who took both doses of the vaccine within 28 days.

The efficacy of this vaccine was demonstrated in a regimen containing 2 doses with an interval of 2 weeks. For the prevention of symptomatic cases of COVID-19 that required outpatient or hospital care, efficacy was 77.96%. There were no serious cases in vaccinated subjects, compared to 7 severe cases in the placebo group.

Considering the absence of co-administration studies, covid-19 vaccines are currently not recommended simultaneously with other vaccines. Thus, a minimum interval of 14

days is recommended between COVID-19 vaccines and the different vaccines of the National Vaccination Calendar.

- Covishield® (AstraZeneca® / Fiocruz):

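### The primary infection outcome uses a symptoms-only case rule for the 80% expected to be COVID-vaccinated, and the plan gives no COVID-vaccination rule for the primary comparison, so a BCG effect on symptoms alone could read as prevented infection

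*Combined protocol and SAP*

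**What the plan says.** All references are to the combined protocol and SAP.

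- **Primary Objectives, item 1:** "Assess the impact of BCG vaccine administration on the cumulative incidence of SARS-CoV-2 infection". The Statistical Analysis Plan and the Interim Analysis Plan use the same outcome, compared between arms.
- **Study visits:** during follow-up, RT-PCR is done when a participant has symptoms. Serology is there to find infections that passed without symptoms, including those that BCG may have attenuated. For COVID-vaccinated people this section drops serology as a way to diagnose asymptomatic infection.
- **Secondary Objectives, closing paragraphs on COVID-19 vaccines:** for vaccinated participants, asymptomatic infection shown by seroconversion at M3 and M6 "will not be evaluated, considering the bias caused by the use of vaccines against viral disease". This is the only place that sets the replacement rule: self-reported symptoms together with a positive RT-PCR.
- **Study Definitions:** an asymptomatic person counts by RT-PCR or by a "reagent result for IgM and/or IgA performed by the following methods: ELISA or Immunochromatography (rapid test) for antibody detection". Study visits also names IgG for this purpose, so the status of an asymptomatic IgG-only conversion is unsettled.
- **Inclusion criteria, item 4:** a participant must "Have not received a specific vaccine against COVID-19 or, if vaccinated against SARS-CoV-2, have received the complete immunization schedule". Vaccination after the study dose is also allowed, so status can change during follow-up.
- **Intent to consider COVID vaccination:** the objectives for the COVID-vaccinated subgroup "will be carried out in the part, taking into account in the future analysis, the time between the intervention of the study and vaccination", and the Comparator section speaks of judging efficacy "considering the use of specific vaccines against COVID-19, the time of positivity of COVID-19 tests and the evolution to severe forms of COVID-19". Neither gives a method.
- **Statistical Analysis Plan:** the only split by COVID vaccine applies to the immunoinflammatory variables. The logistic or robust Poisson model names no covariate, stratum or censoring rule for COVID vaccination.

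**The concern.** The protocol itself treats symptom attenuation by BCG as plausible and uses serology to see past it. It then removes that check for most of the expected sample. In the vaccinated group an infection without symptoms cannot be counted, so a BCG effect on symptoms and a BCG effect on infection give the same result.

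The conclusion at stake is the first primary objective, which is also one of the differences that can stop the trial early. Two secondary objectives come close to a check: whether BCG "prolongs the time to the first respiratory disease proven by SARS-CoV-2", and whether it "reduces the proportion of symptoms associated with COVID-19". Nothing ties either of them to how the primary result is read.

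**Working it through.** **Inputs.** From Sample size: infection risk 30% (unvaccinated) and 15% (COVID-vaccinated), 80% COVID-vaccinated, 376 per arm (taken as given). From Primary Outcome 3: equal uptake by arm and the expected counts. The documents give no symptomatic share among the infected. I assume s0 = 0.6 on placebo and s1 = 0.5 or 0.4 on BCG, and then vary both.

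**1. The plan's expected counts reproduce.** Per arm, 376 × 0.2 = 75.2 unvaccinated and 376 × 0.8 = 300.8 vaccinated.
- BCG only: 75.2 × 0.20 = 15.0 (stated 15)
- Neither vaccine: 75.2 × 0.30 = 22.6 (23)
- COVID vaccine only: 300.8 × 0.15 = 45.1 (45)
- Both: 45.1 × 0.85 = 38.4 (38)

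**2. Where the events come from.** (45 + 38)/(15 + 23 + 45 + 38) = 83/121 = 69% arise where a case needs symptoms. In that group the planned fall is 38/45 = 0.84. A 16% fall in symptoms with no infection prevented would give the same ratio.

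**3. Pooled risk ratio if BCG changes symptoms only.** The strata contribute 0.2 × 0.30 = 0.06 and 0.8 × 0.15 = 0.12. The documents do not settle whether the 15% means true or detected infection, so both readings are shown.
- True reading: RR = (0.06 + 0.12·s1)/(0.06 + 0.12·s0)
- Detected reading: RR = (0.06 + 0.12·s1/s0)/0.18

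The chance of a significant result in BCG's favour uses the normal approximation Φ{[p0 − p1 − z·√(2p̄(1−p̄)/n)] / √[(p0(1−p0) + p1(1−p1))/n]}. The final analysis has n = 376 per arm and z = 1.96. The interim has n = 188 per arm with complete follow-up and the plan's z = 2.78.

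| Reading | s1 | Placebo | BCG | RR | Final | Interim |
|---|---|---|---|---|---|---|
| True | 0.5 | 13.2% | 12.0% | 0.91 | 7% | 1% |
| True | 0.4 | 13.2% | 10.8% | 0.82 | 17% | 2% |
| Detected | 0.5 | 18.0% | 16.0% | 0.89 | 11% | 1% |
| Detected | 0.4 | 18.0% | 14.0% | 0.78 | 32% | 4% |

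The true infection RR is 1.00 in every row, and the nominal final chance in this direction is 2.5%. Over starting shares of 0.5–0.8, falls of 0.1–0.2 and both readings, RR runs from 0.73 to 0.92. With s1 = s0 and equal uptake, RR = 1.00.

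**4. Later COVID vaccination.** The table puts all 80% under the symptom rule throughout. Suppose instead that half of that group's events counted regardless of symptoms (assumed). On the detected reading, RR = (0.06 + 0.06 + 0.06·s1/s0)/0.18 = 0.94 or 0.89, in place of 0.89 or 0.78.

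**5. A uniform symptomatic RT-PCR outcome.** In the same scenario its RR is s1/s0 = 0.83 or 0.67, further from 1 than the pooled result. It makes the definition uniform but cannot expose attenuation.

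**6. Power of that outcome on the plan's counts.** The pooled counts are 68 (23 + 45) against 53 (15 + 38) of 376. With an assumed asymptomatic share a = 0.2–0.5, multiply the unvaccinated counts (detected reading) or all counts (true reading) by 1 − a. Two-sided 5% power is then about 17–28%, against about 28–32% for the pooled outcome.

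**The case against.** **Pooling is not stated.** The paragraph on COVID-vaccinated participants is poorly translated and may mean that they are analysed apart. If so, the pooled ratios do not describe the planned analysis. This stands, and it is why the claim is conditional. It does not remove the gap, because no section sets a rule for the primary comparison.

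**The sizes are assumed and simplified.** This also stands. The documents give neither a symptomatic share nor a BCG effect on symptoms, and later COVID vaccination shrinks the distortion (step 4). The unvaccinated contribution is held at 0.06, as if symptoms had no bearing on detection there. The figures therefore show the result of missing asymptomatic detection and do not isolate the effect of having two rules.

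**Early stopping on this route is unlikely.** Agreed: about 1–4%.

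A reader might also infer stronger points that the documents do not support:
- *The plan ignores COVID vaccination.* It does not. It states an intent to consider it and splits the immune variables by it. The gap is in the primary comparison.
- *The primary result is biased as it stands.* With no BCG effect and equal uptake it is not.
- *Uptake, and so detection, will differ by arm.* The Blinding section lets a participant be unblinded on request and, if on placebo, vaccinated earlier, so a route exists. The plan only assumes equal uptake, but there are no data on any gap.
- *The severe-disease outcome is distorted in the same way.* Severe acute respiratory syndrome is symptomatic under Study Definitions, so dropping asymptomatic serology does not remove severe cases.
- *A uniform symptomatic analysis would settle the matter.* Step 5 shows that it would agree with the wrong reading.

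**Conclusion.** The concern holds in a conditional form, and I hold it with moderate confidence. One primary outcome has two case rules. The rule for asymptomatic IgG-only conversion is inconsistent between Study Definitions and Study visits, and the plan does not say how COVID-vaccinated participants enter the primary comparison.

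If they are pooled, a BCG effect confined to symptoms would appear as an infection RR of about 0.91 to 0.78, with a 7–32% chance of significance at the final analysis. This rests on an assumed fall in symptomatic share from 0.6 to 0.5 or 0.4, on equal 80% uptake, and on the symptom rule applying throughout follow-up. The distortion is smaller if COVID vaccination comes later. What is at risk is the meaning of a positive result. This should be fixed before unblinding, because a rule chosen afterwards could be chosen by its result.

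**What to change.** In the SAP, before unblinding:

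1. State whether COVID-vaccinated and unvaccinated participants are combined in the primary comparison. Report the BCG effect by COVID-vaccination status at inclusion. Reconcile Study Definitions and Study visits on asymptomatic IgG-only conversions.
2. Describe the pooled result as detected infection, symptomatic only in COVID-vaccinated participants. Do not conclude from it alone that BCG prevents infection.
3. Report seroconversion separately as the evidence on infection. Count conversions at scheduled draws before the first COVID-vaccine dose, and censor at the last draw before that dose. No draw is planned at COVID vaccination: for a dose on day 60 the last routine draw is M1, at day 10. State that at the expected uptake this is likely to cover a minority of follow-up, that conversions between the draw and the dose are missed, and that the censoring may be informative.
4. Report symptomatic RT-PCR-confirmed disease in all participants as a uniformly defined supportive outcome. Say that it cannot separate prevention of infection from attenuation of symptoms, and do not use it to support a prevention-of-infection claim.
5. Adjust the primary model for COVID-vaccination status at inclusion, not for vaccination after randomisation. Report uptake and timing by arm.

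The cost is SAP wording and a little more analysis. The primary outcome stays and no visit or test is added. The separate serology and symptomatic analyses will have low power, about 17–28% for the symptomatic one on the plan's own counts.
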